The primary outcome measure and endpoint will be the WOMAC Pain scale measured 1 year following knee arthroplasty.¹⁰⁵⁻¹⁰⁹ The WOMAC has been studied extensively and its scales have been shown to be reliable and valid for quantifying the extent of both pain and disability in patients undergoing knee arthroplasty.^{16,110,111} Secondary outcome measures will be the WOMAC Disability scale, Pain Catastrophizing Scale (PCS),¹¹²⁻¹¹⁴ a verbal pain rating scale,^{115,116} and a patient global rating of change scale measured on a numerical rating scale from -5 (vastly worse) to +5 (completely recovered) and measured 2 months, 6 months and 1 year post-surgery.¹¹⁷⁻¹¹⁹ The timeframes were chosen because the trajectory of recovery following knee arthroplasty is non-linear and we want to track changes associated with the intervention during the course of the study.^{10,13,94} Two performance-based measures, the 6-minute walk test^{93,98} and the Short Physical Performance Battery will be assessed at baseline and 1 year post-surgery.¹²⁰ Routine follow-up visits are typically scheduled with the surgeon at 12 months following surgery. Planning follow-up measures to coincide with routine patient visits to their surgeon or other provider will be a cost-effective and clinically feasible way of collecting follow-up data with minimal burden. All sites will have the space necessary to conduct the performance-based tests. This is the first study of a pain coping skills training intervention that has used performance-based measures to assess efficacy. This battery of primary and secondary outcomes addresses the key domains of outcomes recommended by IMMPACT, a consensus based group of experts in the area of pain treatment outcomes.^{121,122}

Sample Size Estimations

The primary endpoint will be the WOMAC Pain score at 1 year. Changes of 2 or more points in the 20 point WOMAC Pain scale indicate clinically important differences between individual patients.¹²³⁻¹²⁶ We powered our study to detect a difference of at least 2 points between the pain coping skills group and the arthritis education group. Our pilot study showed a larger difference of 4.2 points (with an effect size of .74) between the coping skills group and the usual care group two months following surgery. We will use a more conservative treatment

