effect of 2 WOMAC Pain points for coping skills training for three reasons. First, our pilot study used a quasi-experimental design which may overestimate treatment effects because of non-randomization. Second, estimates were based on comparisons to usual care, and we suspect that some therapeutic benefit will be experienced by the arthritis education group. Third, these data represent only short-term changes following surgery and most patients continue to improve up to a year following surgery.^{9,14}

Using a two-sided two group 0.05-level t-test of differences in means and assuming the intervention difference minus the arthritis education control difference is at least 2.0 WOMAC Pain points, a sample size of 107 in each group will have 91% power to detect this difference, assuming that the common standard deviation is 4.34 (based on pilot work described earlier). This corresponds to an effect size of 0.46 which is consistent with the effect of other behavioral interventions for knee arthritis.¹²⁷⁻¹²⁹ This sample size also adequately powers the study to detect a 20% difference between groups in the number of patients with a 50% or greater improvements in WOMAC pain relative to baseline scores.^{9,10,12-15,130} This effect will be equivalent to an odds ratio of 2.25 and is equivalent to a Numbers Needed to Treat (NNT) of 5 which is indicative of an effective intervention.¹³¹ The revised CONSORT statement endorses use of indexes such as number needed to treat.¹³²

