Thus, the total required sample size is 321 (107 patients per arm) for the planned 3-arm trial. Based on our pilot study, we expect 5% attrition due to early drop-out resulting from cancelled surgery. Patients who undergo surgery and drop out due to lack of interest, unrelated medical illness or loss of follow-up also will be included in the intent to treat analysis. Our pilot study of 18 patients suggests this number will be on the order of 10%, although this estimate is likely to be low because the pilot study was only 2 months in duration. Our previous work with similar types of patients suggests that loss to follow-up will likely be closer to 20% one year following surgery.^{14,29} Therefore, 402 patients (134 patients per study arm) will need to be enrolled in the trial (321+64 due to loss of follow-up+17 due to cancelled surgery). A total of 2,100 patients will need to be screened because our pilot studies indicated that approximately 19% of the screened sample will actually participate (ie. they will meet all inclusion and exclusion criteria AND provide consent for the study). Stratification by surgeon and by site is expected to reduce outcome variability and thereby increase power.

Data Analysis

Intention to treat (ITT) will be the primary approach for all analyses and, depending on the pattern of missing data (missing at random, completely at random or not missing at random), multiple imputation using SAS StAT/MI methods will be used to impute values for those lost to follow-up.¹³³ In addition, we will compare the ITT analysis to the results for patients who actually undergo surgery to determine if undergoing surgery affects the findings. For the primary analysis, the effect of treatment will be assessed using linear mixed models with time as a repeated factor. The model will account for correlation over time within participants, correlations within clinics, surgeons, and baseline covariates. Surgical approach, complications, medication and physical therapy use will be assessed for potential effects.

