Estimates of the effect of pain coping skills training will be obtained by constructing linear contrasts to compare the mean change in outcome from baseline to each of the key time points (2 months, 6 months and 1 year) between the pain coping skills group and the two control groups, with adjustment for the other variables. Analyses of the secondary outcome variables will be conducted using a similar approach. For the analyses using dichotomous outcomes of $\geq 50\%$ improvement at 6 months and 12 months, generalized linear models with logistic regression will be used to compare the proportion of patients with $\geq 50\%$ improvement after adjustment for baseline data.

Our study is powered to detect clinically important differences in WOMAC Pain scores among treatment groups. As an additional secondary analysis, we also will examine the effects of potential moderators. Moderators are baseline characteristics that predict treatment effects.¹³⁴ Additional psychosocial issues may influence treatment effects in knee arthroplasty patients with high levels of pain catastrophizing. Potential

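### The plan does not say how baseline WOMAC Pain enters the primary model; if it is an unconstrained repeated response, the change contrast is unbiased but usually gives up precision that baseline adjustment would recover at no cost

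*Combined protocol and SAP*

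**What the plan says.** Under Data Analysis, "the effect of treatment will be assessed using linear mixed models with time as a repeated factor". The model is to allow for correlation within participants, clinics and surgeons and for baseline covariates, which are not listed. The treatment effect comes from "constructing linear contrasts to compare the mean change in outcome from baseline to each of the key time points". These contrasts set coping skills training against each control arm at three follow-ups, the last of them at 1 year, and adjust for other variables that are not defined. Secondary outcomes follow a similar approach.

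Under Sample Size Estimations, "The primary endpoint will be the WOMAC Pain score at 1 year". The power statement rests on a two-sided t-test at the 5% level and frames the target as a difference of differences: "assuming the intervention difference minus the arthritis education control difference is at least 2.0 WOMAC Pain points". It reports 91% power with 107 patients per arm. The spread is introduced with the words "assuming that the common standard deviation is 4.34 (based on pilot work described earlier"). The text does not say whether 4.34 is the SD of change, of the 1-year score, or a residual SD.

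The section on Specific Aim 2 confirms that WOMAC Pain is collected at every assessment, including before surgery. The levels of the time factor are not listed. No sentence names baseline WOMAC Pain as an adjuster in the primary model, and none says whether baseline means are held equal across arms.

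**The concern.** A contrast of change from baseline inside a repeated-measures model ordinarily means that baseline is one of the time levels, with its own mean in each arm. The powering as a difference of differences points the same way. On that reading the contrast subtracts the whole observed baseline difference between arms, whatever the correlation between baseline and 1 year. Baseline adjustment subtracts only the part that baseline predicts.

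The reference to baseline covariates does not settle the matter. A covariate entered as a main effect shifts all of a patient's time points equally and cancels from a within-patient change. Only a baseline-by-time term, or a common baseline mean for all arms, would alter the contrast.

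At stake is the standard error of both primary comparisons (against arthritis education and against usual care) and of the secondary outcomes that have a baseline value.

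**Working it through.** **Inputs from the documents.** 107 per arm, difference 2.0 points, SD 4.34, two-sided 5% level (Sample Size Estimations). Pilot SDs of improvement 4.7 (n = 18) and 4.8 (n = 45) (Pilot Intervention Study). Entry requires WOMAC Pain of at least 5 (inclusion criteria).

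**Assumed, because the documents do not give them.** r, the correlation of baseline with 1-year WOMAC Pain, from 0.2 to 0.5. k = SD(baseline)/SD(1 year), at 1, 0.8 and 0.6. Values below 1 are considered because the entry threshold may narrow the baseline spread.

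**1. The plan's own figure.** 2/4.34 = 0.461, matching the stated 0.46. The standard error is 4.34 × √(2/107) = 0.593, and 2/0.593 = 3.37. Power is 91.9% (noncentral t) or 92.1% (normal approximation), against the stated 91%. The figure reproduces.

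**2. Variance of the two contrasts.** Let D0 and D1 be the between-arm differences in means at baseline and 1 year, and s the 1-year SD. The estimator D1 − b·D0 has variance (2/n)·s²·(1 + b²k² − 2brk).
- Change score, b = 1: (2/n)·s²·(k² + 1 − 2rk).
- Baseline-adjusted, b = r/k: (2/n)·s²·(1 − r²).

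The change-score variance minus the adjusted variance is (2/n)·s²·(k − r)². Adjustment is therefore never worse in large samples, and there is no gain when r = k. The variance ratio, adjusted to change, is (1 − r²)/(k² + 1 − 2rk). With k = 1 it reduces to (1 + r)/2.

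**3. Ratio, and power if 4.34 is the SD of change.** The adjusted SD is 4.34 × √ratio. The comparator is 91.9%.

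| r | k = 1 | k = 0.8 | k = 0.6 |
|---|---|---|---|
| 0.2 | 0.60, 99.1% | 0.73, 97.6% | 0.86, 95.2% |
| 0.3 | 0.65, 98.6% | 0.78, 96.6% | 0.91, 94.0% |
| 0.5 | 0.75, 97.2% | 0.89, 94.4% | 0.99, 92.2% |

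Example, r = 0.3 and k = 0.8: (1 − 0.09)/(0.64 + 1 − 0.48) = 0.91/1.16 = 0.78.

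**4. Simulation check.** 4,000 trials, four time points, complete data, equal SDs, r = 0.4, SD of change 4.34. Empirical SEs were 0.590 for the change contrast, 0.498 for baseline as covariate and 0.497 for constrained baseline means. (0.498/0.590)² = 0.71, against the expected (1 + 0.4)/2 = 0.70. In one simulated data set with baseline as a response, adding baseline as a main-effect covariate left the change contrast at −1.896, exactly as without it.

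**5. Sensitivity to what 4.34 is.**
- The pooled pilot SD of improvement is √((17 × 4.7² + 44 × 4.8²)/61) = 4.77, at which the change contrast has about 86% power.
- If 4.34 is the SD of the 1-year score and k = 1, the change contrast has 75.6% power at r = 0.2 and 91.9% at r = 0.5. The adjusted contrast has 92.8% and 97.2%.
- If 4.34 is already a baseline-adjusted residual SD, then 92% is the power of the adjusted analysis and no further gain may be added to it.

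These powers ignore clustering by surgeon and clinic, as the plan's own calculation does.

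**The case against.** The strongest reply is that the plan may already adjust. It lists baseline covariates without naming them. If the responses are follow-up or change scores and baseline WOMAC Pain is among those covariates, the analysis is already an analysis of covariance. If baseline is a response with a common mean, nothing material is lost either. The team's habits lend this some support: the pilot was analysed by ANCOVA on baseline scores while its effect was described as a group-by-time interaction, and the responder analysis is adjusted for baseline data. This stands, to the extent that an unconstrained baseline response is an inference, though the natural one. It does not remove the need for the sentence that would settle it.

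Two further points stand. First, the gain depends on k as well as r. A reader might take the equal-SD column, 97-99% power, as the expected benefit, but the entry threshold is a reason to doubt equal SDs, and at k = 0.6 the gain is small. Second, keeping baseline as a response has a benefit: with about 20% loss to follow-up expected, patients with only a baseline value stay in the likelihood. The equality with a raw change-score comparison is also exact only for complete data.

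**Conclusion.** This is an efficiency and specification point, not an error. The plan leaves the role of baseline WOMAC Pain in the primary model open. On the natural reading the adjusted contrast would have 0.60 to 0.99 of the variance of the planned one, for r between 0.2 and 0.5 and k between 0.6 and 1. Power would be between 92% and 99% instead of about 92%, provided 4.34 is the SD of change. Where in that range the trial lies cannot be determined from the documents.

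A reader might infer that the primary analysis is biased or that the trial misses its power target. Neither follows: randomisation makes the change contrast unbiased, and the stated 91% reproduces if 4.34 is the SD of change. Nor do the documents establish that an inefficient analysis was chosen; they fail to exclude it.

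**What to change.** State in Data Analysis that the primary contrast for each comparison is the baseline-adjusted difference in WOMAC Pain at 1 year, and name the model. Either form will do:

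- Baseline and follow-up scores as responses, with baseline means constrained equal across arms. This keeps patients who have only a baseline value and is the simpler choice given the expected loss to follow-up.
- Post-baseline scores only as responses, with baseline WOMAC Pain and its interaction with time as covariates, paired with the multiple imputation already planned so that patients without follow-up are retained.

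Apply the same rule to the secondary outcomes that have a baseline value. The global rating of change has none and is unaffected. Also say which SD 4.34 is and how it was obtained from the pilot.

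Under randomisation the target is unchanged, since the arm difference in mean change equals the arm difference in 1-year means. The cost is a few sentences in the plan, with no new data, visits or patients. Label: free improvement.

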Participants who meet study inclusion criteria and consent to participate will be stratified by orthopaedic surgeon and randomized in permuted blocks of 3, one to each study group, to ensure that patients from each participating physician and site have an equal chance of being randomized to one of the 3 groups. Given that we will have 30 orthopaedic surgeons participating in the study (see Table 5 below), this approach will control for temporal and clustering effects resulting from single surgeons having imbalances in the numbers of patients in each treatment group over time. Assignment to one of the 3 groups will be accomplished with a computer generated table of random numbers created by the biostatistician and provided to the study coordinators at each site via a secure website. After collecting baseline data, each site's study coordinator will conduct treatment allocation by use of the study web site, allowing the treating surgeon and the follow-up data collectors (site coordinators and research assistants) to be blinded. We will instruct all surgeons of the importance of avoiding study contamination by not querying patients about study interventions. Surgeons also will be asked to report if they became aware of group assignment during the study. These data will be tracked and reported at the end of the study.

All data collected at each site will be obtained by data collectors who are blinded to group allocation. This will be accomplished by assigning patients to one of the three treatment groups using a secure website and then providing patients with treatment allocation information in random number matched pre-sealed opaque envelopes. Patients will be instructed to open envelopes once they return home and they will be asked not to mention their group assignment to the data collectors. Information in the envelopes will inform patients about group assignment and will instruct patients to contact site PIs if they have any questions about the treatment to which they have been assigned. Because site PIs will not be collecting data from patients, we will optimize the likelihood of keeping data collectors blinded to group allocation during the course of study.

Interventions

Pain Coping Skills Training

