We recruited a consecutive series of 10 patients 1 year following knee arthroplasty to determine if the SPPB and the six minute walk test would be well tolerated. In addition, we were concerned about possible ceiling effects on the SPPB which can occur with high functioning elderly persons.¹⁰² SPPB total scores range from 0 to 12. The mean score on the SPPB summary scale for the patients was 8.5 (sd = 2.3) and ranged from 3 to 11. We concluded that the SPPB and the 6-minute walk test are well tolerated by patients receiving knee arthroplasty and that some individual tests comprising the SPPB will likely demonstrate ceiling effects. We will therefore use the composite SPPB score and a time-based calculation of the composite SPPB score¹⁰³ in addition to the 6-minute walk test.

Primary and Secondary Outcome Measures and Endpoints

Participants from all three arms will be evaluated by an assessor who is blinded to group allocation at baseline, 1 week prior, and 1 week after, 2 months, 6 months and 1 year after surgery. The baseline assessment will include age, gender, comorbidity^{14,104}, education and occupation, current medications, mental healthcare received and a variety of pain and psychological characteristics including depression, anxiety, pain coping etc. Follow-up outcomes will include measures of pain, function, catastrophizing and depression. (see MOOP in appendix for a complete description).

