moderators for patients with knee arthroplasty who may particularly benefit from pain coping skills training are the following: expectations prior to surgery¹³⁵⁻¹³⁷, self efficacy^{138,139}, extent of social support^{9,140} and depression.²⁷ Recent evidence suggests that psychological states of depression, low expectations for recovery from surgery, poor self-efficacy and reduced social support increase risk of poor outcome following surgery, and may therefore modify the effects of pain coping skills training. Because our study is not powered to test for these potential moderators, they will be assessed only for the primary outcome of WOMAC Pain at 1 year. This analysis will be performed by including a three-way Moderator X Treatment group X Time interaction term in the mixed models analyses. It is our intent to assess whether these variables independently predict those patients who are more likely to respond to pain coping skills training versus arthritis education or usual care. Pain coping skills training emphasizes pain coping strategies, unlike usual care or arthritis education and because of this emphasis, we suspected that coping strategies training would be particularly effective in patients with less healthy psychosocial features. Knowing whether any of these potential moderators actually predict response to treatment will aid in better identifying individuals who are more likely to respond to the intervention.

Cost Analysis

We will conduct a cost analysis to compare mean total costs incurred over the one year follow-up period in the KASTpain study between patients randomized to coping skills training vs. arthritis care (and vs. usual care). We will compare each component (medical costs and indirect costs) and estimate intervention costs. All three components will comprise total costs which will also be compared. Total costs, from the societal perspective, will consist of direct medical costs, intervention-related costs and indirect costs. From the health care system (or payer) perspective, indirect costs will be excluded. Sensitivity analyses will be performed to evaluate the impact of scaling up the intervention (i.e. more patients per session; fixed costs allocated over more patients) and methodological choices for cost assignment.^{141,142}

Cost-Effectiveness Analysis

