The incremental cost effectiveness ratio (ICER) will be calculated as the difference in the mean cost per patient between study arms divided by the difference in estimated quality-adjusted life-years (QALYs). Mean costs will be estimated as described above. Quality-adjusted life-years will be estimated using utility estimates derived from the EQ-5D. Because the interventions represent fixed-, one-time costs while the benefits of the interventions may last beyond the one year follow-up period in the KASTpain study, we will conduct sensitivity analyses that extrapolate differences in utilities measured at the end of follow-up over 3, 5, and 10 years, assuming that the interventions do not differentially impact survival. If we observe statistically significant differences in costs (not including intervention costs) between treatment arms at 12 months, we will extrapolate treatment-specific cost estimates over 3, 5, and 10 years, consistent with the time period for QALYs. We will evaluate uncertainty by estimating 95% CIs for estimates of costs, QALYs and measures of cost-effectiveness (i.e. ICERs or net health benefits¹⁴³) using nonparametric bootstrapping.^{141,142}

Timetable and Milestone Plan

The milestone plan is as follows:

Enrollment of the first subject: Prior to enrolling the first subject, all sites will be required to complete IRB approval procedures and interview, hire and train research staff including the clinical psychologists and nurse educators. All study staff will be required to complete training in the study protocol as described in the MOOP and will also require time to develop working relationships with orthopaedic surgery staff in preparation for patient recruitment and retention. Clinical psychologist training will require travel to Duke University while the PI will travel to each site to train the nurse educators. We expect to have all IRB, hiring and training procedures

completed and should be fully prepared to begin study recruitment within 6 months of the beginning of the study. Assuming that the study will begin on April 1, 2012, the first subject will be recruited by October 1, 2012.

[figure not shown]
25%, 50%, 75% and 100% enrollment projections: We expect enrollment for these various thresholds to occur by the following time periods listed on Table 4 below. The recruitment period will require, at maximum, a total of 3 years.

Table 4 Summary of Recruitment Goals

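### The cost comparison and ICER numerator are specified without the surgeon strata or collected baseline variables; if these predict cost, the reported intervals are somewhat wider than needed.

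*Combined protocol and SAP*

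**What the plan says.** The Cost Analysis section plans to "compare mean total costs incurred over the one year follow-up period in the KASTpain study between patients randomized to coping skills training" and each control, in total and by component. The Cost-Effectiveness Analysis section takes the ICER numerator "calculated as the difference in the mean cost per patient between study arms" and adds: "Mean costs will be estimated as described above". Nothing above that sentence gives an estimator beyond the comparison of means. On uncertainty the same section says: "We will evaluate uncertainty by estimating 95% CIs for estimates of costs, QALYs and measures of cost-effectiveness". The method is a nonparametric bootstrap, and no stratified resampling is mentioned.

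Three other places bear on this:

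- **Randomization and Blinding:** patients are "stratified by orthopaedic surgeon and randomized in permuted blocks of 3", with 30 surgeons.
- **Primary and Secondary Outcome Measures and Endpoints:** "The baseline assessment will include age, gender, comorbidity", and the list goes on to current medications and mental healthcare received. Allocation follows baseline data collection, so these variables are pre-randomisation.
- **Data Analysis:** the primary mixed model accounts for clinic, surgeon and baseline covariates, and secondary outcomes are handled similarly. Costs belong to Hypothesis 3, which the Specific Aims call tertiary, and they are not among the listed secondary outcomes. That wording therefore does not reach them.

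**The concern.** Permuted blocks within surgeon balance the arms on whatever differs between surgeons. An analysis that leaves surgeon out still counts between-surgeon cost variation as error, so its standard error tends to overstate the sampling variability. Baseline variables that predict cost are a separate matter: leaving them out gives up real precision.

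Hypothesis 3 is read from these intervals. The plan also extrapolates treatment-specific costs to 3, 5 and 10 years only if the 12-month cost difference is statistically significant, so the width of the cost interval helps decide whether that extrapolation is run. An unstated cost model can also be chosen after the data are seen.

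**Working it through.** **The plan's own figures.** The documents give no SD, power or interval width for costs. Their only power figure is for WOMAC Pain: 107 per arm, difference 2.0, SD 4.34, two-sided 0.05, stated as 91%. It recomputes to about 92%, so it reproduces, but it says nothing about costs.

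**Inputs from the documents.** 402 enrolled, 134 per arm; 20% loss, so 107 per arm (Sample Size Estimations). 30 surgeons, split 3, 12, 7 and 8 across sites with 100 or 101 patients each (Table 5). Blocks of 3.

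**Assumed.** Skewed costs; a share s of cost variance explained by surgeon plus site; a share c explained by baseline covariates.

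**Raw interval.** Half-width = 1.96 × SD × √(2/107) = 0.268 SD, where SD is the unknown cost SD.

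**Adjusted interval.** Ideal adjustment multiplies the SE by √(1 − s − c). Fitting the extra terms costs something: in simulation with 20% loss, about 1.4% for surgeon terms and 0.3% for site terms when nothing predicts cost. With surgeon terms, the raw/adjusted SE ratio is therefore about [1/√(1 − s − c)] / 1.014.

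| Strata s + covariate c | 1/√(1 − s − c) | Divided by 1.014 | Simulated, 20% loss |
|---|---|---|---|
| 0 + 0 | 1.000 | 0.986 | about 0.987 |
| 2% + 2% | 1.021 | 1.007 | 1.005 |
| 5% + 5% | 1.054 | 1.040 | 1.04 |
| 10% + 10% | 1.118 | 1.103 | 1.09 |
| 5% + 15% | 1.118 | 1.103 | 1.10 |

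The half-width falls from 0.268 SD to 0.268/1.04 = 0.258 SD at 5% + 5%, and to 0.268/1.09 = 0.246 SD at 10% + 10%. Site terms plus the covariate, without surgeon terms, gave ratios of 1.04 to 1.10 in the simulated scenarios with a covariate.

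**Which part is true precision.** Because of the blocking, the raw difference has a true variance of about SD²(1 − s) × 2/n, while its usual SE reports SD² × 2/n.

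- Reported over true SE of the raw difference, 1/√(1 − s): 1.026 at s = 5%, 1.054 at s = 10%. This is conservatism only.
- True SE, raw over adjusted, √[(1 − s)/(1 − s − c)]: √(0.95/0.90) = 1.027 at 5% + 5%; √(0.90/0.80) = 1.061 at 10% + 10%, before the cost of fitting. This comes from the covariate.

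Simulation with strata alone agrees. The sampling SDs of the raw and surgeon-adjusted differences were 0.1134 and 0.1133 at s = 10%, and 0.1143 and 0.1135 at s = 20%.

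**Coverage.** Simulated coverage of the unadjusted 95% interval ran from about 94% to 97% according to the assumed shares and interval type. Over-coverage appears only when the strata explain a good deal of cost.

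**Bootstrap cells.** Resampling within surgeon-by-arm leaves 402/90 = 4.47 patients per cell and shrinks the SE by √(3.47/4.47) = 0.88. Site-by-arm leaves 402/12 = 33.5 per cell, with factor √(32.5/33.5) = 0.985.

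**The case against.** The strongest reply is that the plan is silent and has not decided against adjustment. An ICER is by definition one mean difference over another, and a model can supply either. This stands: a reader might infer that adjustment is ruled out, and the documents do not say so. But as written they commit to nothing beyond a comparison of means, while the clinical outcomes have a stated adjusted model.

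Second, the gain is conditional. No cost variance share is given. Inpatient care is priced from Medicare DRG rates, which may limit variation between surgeons and sites. The length-of-stay adjustment is a costing step on a post-randomisation quantity, so it is no evidence of a baseline predictor. Prior cost or resource use is not listed at baseline. The sentence "Stratification by surgeon and by site is expected to reduce outcome variability and thereby increase power" comes from the WOMAC Pain sample-size paragraph and is not about cost. All of this stands, and it limits how large a gain can be claimed.

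Third, 30 surgeon terms can cost more than they return. One simulation gave intervals about 5% wider when nothing predicts cost. It fitted only the two arms compared and set a t interval against a percentile bootstrap interval; the sampling SD itself rose 3% (0.1391/0.1350). Using all three arms and comparing SEs, the penalty is about 1.4%, and 0.3% with site terms. The point favours site terms or a random surgeon effect; it does not favour leaving adjustment out.

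Last, costs are a tertiary hypothesis with no power claim, and any error is mainly on the conservative side. That is a fair reason to rank the point below anything affecting WOMAC Pain.

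**Conclusion.** The point holds as a conditional efficiency and specification gap. The cost comparison and ICER numerator are written without the randomisation strata or collected baseline variables. If these predict cost, the reported intervals are somewhat wider than needed: about 4% to 9% in SE for assumed shares of 5% + 5% to 10% + 10% with 20% loss, and about nothing at 2% + 2% or below. There is no bias.

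Two stronger readings are tempting. A reader might infer that the intervals are certainly too wide; without a cost variance share, the documents cannot show that. A reader might also square the SE ratios (1.04² = 1.08, 1.09² = 1.19) and conclude that the plan throws away 8% to 19% of its patients' worth of precision. That overstates the loss, because blocking already protects the raw estimate from stratum differences. On true precision the ratios are 0.95/0.90 = 1.06 and 0.90/0.80 = 1.125, before the cost of fitting, and they rest wholly on the assumed covariate.

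The ICER interval also depends on the QALY difference, so it need not narrow in proportion to the cost interval.

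**What to change.** In the Cost Analysis and Cost-Effectiveness Analysis sections:

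1. Estimate each cost difference (medical, indirect, total and the ICER numerator) from a prespecified linear model of patient cost on arm, site (or surgeon as a random effect), and a few named baseline covariates: age, comorbidity and current medications.
2. Estimate the QALY difference in the same way, adding baseline EQ-5D utility if it is collected, so that numerator and denominator use matching estimators. The Economic Evaluation section gives no EQ-5D schedule, so the SAP should state it.
3. Bootstrap patients within site-by-arm, keep each patient's cost and QALY together, and refit both models in each replicate. Do not resample within surgeon-by-arm cells.
4. Show the raw arm means alongside.

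The cost is SAP wording and slightly more analysis work. The cost model needs no new data. If the variables turn out not to predict cost, the interval is about 0 to 1.5% wider.
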